Study Protocol and Statistical Analysis Plan

Mobile Behavioral Parent Training for Childhood ADHD: A Micro-randomized Trial

NCT06012851

Last Date Updated and Approved: August 7, 2024

Study Protocol

Overview

The current study aims to leverage an established data collection and intervention development smartphone application to develop and pilot a mobile behavioral parent training (BPT) intervention for parents of children with ADHD and academic difficulties. The intervention will target candidate mechanisms of child behavioral and academic success including parenting skills, parent academic management, and engagement with treatment material. mBPT will include: 1) online, asynchronous treatment videos, 2) survey data collection, 3) prompts to complete between session parent practice, and 4) personalized adaptive components to enhance parenting skills.

First, we will determine appropriate tailoring variables and decision rules for intervention personalization (Aim 1). Second (Aim 2), we will conduct a micro-randomized trial to refine the intervention and determine which micro-interventions should be included in the refined intervention. Finally (Aim 3), we will conduct a randomized, controlled pilot trial to compare the mBPT with mBPT combined with personalized, adaptive micro-interventions (JITAI).

The current IRB protocol pertains to the Aim 2 micro-randomized trial.

Procedures: Participants will be children with ADHD and their families. They will be invited to attend a brief virtual or in-person meeting to provide informed consent, complete assessment materials to confirm eligibility, provide baseline measures, and facilitate the child's teacher completing baseline measures of symptoms and impairment. If the child meets eligibility criteria, parents will then be provided access to the developed beta-mBPT program on their smartphones and will agree to be audio-recorded for 60 minutes per day for 28 days. The audio-recordings will be used to trigger immediate, personalized feedback (micro-interventions) to be delivered via phone to the parent--similar to receiving a prompt to stand up when a smartwatch detects that someone has been sitting for a long time. The effects of these micro-interventions on parent and child behavior will be examined. Parents will also have the option to provide more detailed, daily feedback on the application and intervention for a maximum of seven days during the study for additional compensation.

The primary possible risk is loss of confidentiality, and the primary possible benefit is improvement in parent/child relationship and child functioning. If the intervention is found to be effective, this research has the potential to relieve the public mental health burden of childhood ADHD.

Objective and Analyses: We aim to examine the effects of brief, parent-directed micro-interventions sent to a parent's phone while they are interacting with their child. To do this, we will conduct a micro-randomized trial in which parents are randomized to receive or not receive the micro-intervention repeatedly. There will be a total of 9 possible randomization opportunities per participant per day. We will then evaluate whether parent and child behavior

is significantly different when the parent was randomized to receive the micro-intervention (prompt) or not. We hypothesize that following parenting feedback delivered via the phone application, the parent-child interaction will be more positive and less negative compared to when the parent was not provided feedback. We will also examine the usability and feasibility of this intervention method.

Subjects

Duration of Participation: Total active time commitment is estimated to be about 7-8 hours. This includes consent and baseline assessment (60-120 minutes), about 45-60 minutes of intervention engagement weekly over 4 weeks (about 4 hours total), 10 minutes monthly for phone calls (30 minutes total), and 45-60 minutes for post-treatment assessment.

Additionally, there will be approximately 28 hours (one hour per day for 4 weeks) of passive data collection including audio data.

Optional Journaling: Participants will be able to opt-in to provide up to 7 days of journaling (more detailed, daily reports of application use) during the study for additional compensation. This will take approximately 5-10 minutes per day for an estimated 35-70 total minutes during the study.

Justification for Number of Participants: We predict that there will be a medium effect size on parenting skills. A recent meta-analysis (Charach et al., 2013) reported an average effect size of .55 for proximal outcomes (i.e., parenting behaviors) and an average effect size of .75 for distal outcomes (i.e., child behaviors) for parent training studies. Prinz and colleagues (2021) recently reported that online, self-directed BPT was not inferior to in-person treatment, and self-directed parenting programs have been shown to produce medium, positive effects on child behavior (Baumel et al., 2017). Power analysis for the Aim 2 micro-randomized trial was conducted with R (version 4.1.3; MRTSampleSize package). With an estimated 28 days per family in the trial, randomization probability of 50% for receiving a micro-intervention, a decreasing linear trend of micro-intervention effects with a medium effect size, and constant availability estimated to be 60% (given targeted decision points), $n = 30$ families are needed (Liao et al., 2016), and we aim to recruit $n = 33$ to ensure sufficient power.

Characteristics of Participants: Study participants will consist of 33 families. Each family will include one child, ages 7-12, with ADHD and up to two caregivers (total of up to 99 people in the study). This population is justified as the treatment being evaluated aims to target parenting among parents of children with ADHD to improve parent skills, functioning, and child functioning. Childhood ADHD is a prevalent, persistent, and impairing disorder, and intervening may improve the outcomes for children with ADHD and their families. Similar interventions have been shown to be effective.

Inclusion and Exclusion Criteria: Inclusion criteria: 1) currently meets DSM-5 diagnostic criteria for ADHD, 2) ages 7 -12, 3) has parent or teacher-rated impairment in homework performance defined as a score of 3 or greater on an Impairment Rating Scale measure (Fabiano et al., 2006)

of homework performance, and 4) has at least one parent or primary caregiver who is willing to participate and is able to access the intervention at home via smartphone. Eligibility for participation will not be affected by current or past pharmacological treatment for ADHD or other diagnoses. Adverse events and changes in treatment will be assessed during monthly phone calls.

This population is justified as the treatment being evaluated aims to target parenting among parents of children with ADHD to improve parent skills, functioning, and child functioning. The age range is when ADHD is most often diagnosed and when parents are most often seeking treatment for their families (Danielson et al., 2019). The intervention will also target homework and academic difficulties at home.

Parental/Child Consent Process: Potential families will be contacted by an experimenter and will be screened via telephone to determine basic eligibility (age, child diagnosis). Families will attend virtual or in-person meeting and provide consent/assent. Families that meet eligibility will be invited to participate and complete questionnaires of study measures.

At the beginning of the visit, study personnel will go over the consent form in detail. All procedures will be clearly explained to caregivers so that they clearly understand (1) what data are being measured and when, (2) any potential risks and benefits, and (3) the limits of confidentiality. After providing written consent, caregivers will also provide consent on the smartphone app. This additional app-based consent form will notify participants of each type of data collected and will request consent and permissions for accessing data on their devices (consent will include adult consent, child assent, and parental consent). We will employ understandable informed consent procedures so that participants can see what data are collected, which will contribute to industry standards for transparency, participant control, and participant ownership of data.

Experimenters will obtain adult consent, parental consent, and child assent for the collection of child data, in line with HHS and OHRS requirements. Children and parents will be approached together. Each parent/caregiver who is participating must provide their own consent to participate. Caregivers will be given the opportunity to read all consent documents and to ask questions and express any concerns. No procedures will be conducted until caregivers have provided both written and app-based consent. Participants will be informed that they can request that any or all of their data be deleted at any time; may listen to, read, and/or delete any recordings or text files that are collected; may skip any questions; and that they can pause or stop their participation at any time (via the mute, pause, and stop data collection functions easily accessible from the app) and/or via contacting study staff via e-mail, phone, or letter.

Description of Compensation or Incentives: Parents will receive a \$50 gift card for participating. This can be broken down into \$10 per week of sufficient data collection (two-thirds of passive data collected) over 4 weeks with an additional \$10 provided if all 4 weeks of data are provided. Parents who opt to participate in the one week of journaling will receive \$10

per day that the daily journaling form is completed and submitted for up to \$70 in addition to the \$50 compensation for the study.

Methods and Activities

Description of Methods and Activities:

1. Parents and children will attend the consent/assent and intake appointment virtually via Zoom or in person. Together with study staff, parents will review the privacy policy for Colliga Apps. Parents will also complete the teacher release form so study staff can request teacher ratings. Parents will indicate on the consent form whether they would like to complete daily journaling for up to seven days during the study.

2. After consent/assent, parents will complete baseline measures on provided iPads or via secure, individual survey links on their own devices. Baseline, parent report measures include: Family Information Form for demographics; disruptive behavior disorders rating scale as a measure of child ADHD symptoms; Homework problems checklist and homework routine measure to measure child behaviors during homework time and the homework routine; Impairment Rating Scale to measure child impairment; Strengths and difficulties questionnaire to measure overall mental health functioning among child participants; Alabama Parenting Questionnaire- short form that measures parenting strategies; Barriers to treatment participation scales to measure reasons for difficulty engaging in treatment; Parent motivation inventory to measure caregiver motivation to engage in treatment; Parenting Stress Index- Short Form to measure parenting stress; Knowledge of Parenting Strategies Scale to measure baseline parenting skills knowledge; Patient Health Questionnaire-9 to assess parent mental health; Adult ADHD Self-Report Scale to measure parent self-report of ADHD symptoms. Ph.D. level psychologist will then conduct a brief, semi-structured interview to determine ADHD diagnosis. The psychologist will also screen for suicidal thoughts and behaviors.

3. Ratings will also be sent to teachers. Teachers will complete ratings of ADHD symptoms, impairment, child difficulties related to mental health, and academic functioning at baseline. ADHD symptoms and impairment ratings inform diagnosis.

4. Participants will be guided on how to download the Colliga App on their phones where all interventions will be housed and where passive audio recording and data collection will occur. They will complete the in-application consent form, and we will also assist them in becoming familiar with the intervention components in the application. We will modify this to be responsive to emergent questions or clarifications as we enroll subjects to ensure procedures are clear and transparent.

5. Four weeks continuous participation: Parents will schedule times for their phone to record for 60 minutes per day for four consecutive weeks (a total of 28 hours of recording). They will also have access to the beta, 4-week version of the mobile behavioral parent training intervention. During the study, the phone will use passively collected data, including audio data, to detect key states (for example, overall negative or positive state). These will be detected

every 6-minutes during audio data collection. Following each 6-minute interval, the parent/child dyad will be randomized to one of three conditions, (1) no intervention; (2) Parenting Behavior Strategy (e.g., suggestion to catch the child being good or provide clear instructions); (3) Parent-Focused Feedback (e.g., feedback regarding positive parenting skill use). Tailoring variables affecting the personalization of the micro-intervention include: sensitivity analysis and key words evaluated in the preceding six minutes. Given one hour per day of recorded interaction, each parent/child dyad will have up to 9 randomization opportunities daily, and will receive an average of 6 micro-interventions each day (if they approve the audio recording).

6. Parents who opt to complete daily journaling for up to 7 days during the four-week study will receive the journaling measure for one week each. This will be planned for the first 7 days of their study enrollment, but can be flexible based on family preference and research staff needs to facilitate staff ensuring daily receipt of journals.

7. Parents will be called at the end of the study to assess for adverse events and will be provided the gift card(s). Measures of symptoms, impairment, family functioning, etc will not be collected at the end of the study given the focus on proximal changes in parent behavior as the primary outcome. Parents will complete the System Usability Survey, Mobile Application Rating Scale, and the Exit Interview to provide information on the usability and feasibility of the application and intervention.

Statistical Analysis Plan

Overview: This study is a micro-randomized trial (MRT) evaluating whether in-the-moment smartphone notifications (personalized parenting suggestions or personalized feedback) improve proximal parenting behavior among caregivers of children with ADHD. During up to two daily audio-recording sessions, caregivers are randomized every 6 minutes to: (a) no notification (50%), (b) suggestion (25%), or (c) feedback (25%). The proximal outcome is a binary indicator of positive parenting sentiment in the subsequent 6-minute window.

Primary Outcome: Binary indicator of positive sentiment (i.e., positive sentiment vs. negative or neutral sentiment) measured in the 6-minute epoch following each randomization decision point in the micro-randomized trial. Additionally, the binary indicator of negative sentiment measured in the 6-minute epoch following each randomization decision point will be examined as an outcome.

Primary Comparison: The marginal causal excursion effect of receiving any active micro-intervention (suggestion or feedback) versus no notification on the proximal binary outcome. Secondly, we will examine potential effects of micro-intervention type (feedback vs. suggestion/strategy) on sentiment.

Mean Differences: Means and standard deviations for outcome measures by micro-intervention condition are provided in clinicaltrials.gov.

Primary Analysis: A weighted, centered logistic regression model for binary proximal outcomes, implemented using the MRTAnalysis R package (D3C, University of Michigan). The model incorporates known randomization probabilities, participant-level clustering, and time-varying covariates as needed. Availability at each decision point will not be included in models as the participants have indicated availability by starting the recording (i.e., micro-interventions are only delivered within 30 minutes of participant starting audio-recording). The primary coefficient estimates the causal excursion log-odds ratio for active micro-intervention vs. no notification. Analyses are not aimed at determining significance given the small sample size and the pilot nature of the research study. Direction of effects, means, and user feedback and key outcomes.

Secondary Analyses: Moderated causal excursion effects will examine whether treatment effects vary by factors that are static such as child age and oppositional defiant disorder symptoms at baseline, and time-varying moderators including progress in asynchronous treatment (i.e., behavioral treatment modules) and sentiment immediately prior to randomization. All secondary analyses are exploratory.

Missing Data: Decision points without valid audio or outcome coding will be excluded from primary analyses. Sensitivity analyses will be conducted including only micro-intervention instances in which users confirmed micro-intervention receipt on their phone (as well as the no micro-intervention condition). Given availability, missingness is low.

Software: All analyses will be performed in R, using the MRTAnalysis package for estimation of marginal and moderated causal excursion effects for binary proximal outcomes.

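### Aim 2 must choose between micro-interventions, but no modelled estimate of suggestion versus none or feedback versus none, with an interval, is planned

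*Combined protocol and SAP*

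**What the plan says.** - **Question.** The protocol Overview says that the Aim 2 micro-randomized trial is to refine the intervention and "determine which micro-interventions should be included in the refined intervention". Aim 3 then tests the result.
- **Conditions.** Description of Methods and Activities, item 5, randomizes each dyad after every 6-minute interval to no intervention, a parenting strategy suggestion, or parent-focused feedback. The SAP Overview gives the probabilities as 50%, 25% and 25%.
- **Primary contrast.** "The marginal causal excursion effect of receiving any active micro-intervention (suggestion or feedback) versus no notification on the proximal binary outcome". The SAP's Primary Analysis reduces this to one parameter: "The primary coefficient estimates the causal excursion log-odds ratio for active micro-intervention vs. no notification".
- **Type contrast.** "Secondly, we will examine potential effects of micro-intervention type (feedback vs. suggestion/strategy) on sentiment".
- **Descriptive results.** "Means and standard deviations for outcome measures by micro-intervention condition are provided in clinicaltrials.gov".
- **How results will be read.** "Analyses are not aimed at determining significance given the small sample size and the pilot nature of the research study". The next sentence, which seems to have lost a verb, lists what counts instead: "Direction of effects, means, and user feedback and key outcomes".

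Secondary Analyses adds moderators, and Missing Data adds a sensitivity analysis restricted to confirmed receipt. Neither section adds a suggestion-versus-none or feedback-versus-none model. No section says what result would lead to a type being included or left out.

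**The concern.** A decision on whether a type belongs in the refined intervention turns on how that type compares with sending nothing. Neither modelled contrast, taken alone, gives that comparison.

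The pooled effect is close to an average of the two type effects. A modest positive value fits two useful types equally well, or one useful type and one that does nothing or harms. A value near zero can hide a useful type. The feedback-versus-suggestion effect is a difference: a gap of 8 percentage points in favour of suggestion arises from +8 and 0, and also from +4 and -4.

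At stake is what Aim 3 tests. Without a modelled estimate and interval for each type, the team would judge each one from raw condition means, which carry no measure of uncertainty that allows for repeated decision points within families, or from arithmetic on two coefficients that the SAP does not describe.

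**Working it through.** **1. The plan's own figure.** Justification for Number of Participants states that 30 families are needed (33 to be recruited), using a 50% probability of any micro-intervention, 28 days, 60% availability and a medium effect that declines linearly. Alpha, power, the standardized effect, its initial value and the number of decision points per day used are not given, so 30 can be neither confirmed nor refuted. With the standard micro-randomized trial formula for a continuous outcome, alpha 0.05 and power 0.80 or 0.90 (all assumed), 30 fits a mean standardized effect of about 0.08 to 0.11 at 9 points per day, or 0.25 to 0.34 at 1 point per day. The stated 50% probability is that of the pooled contrast.

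**2. Relative precision under 50/25/25.** For a contrast of two conditions with probabilities p1 and p2, the variance is proportional to 1/p1 + 1/p2:

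| Contrast | Calculation | Units | Relative to pooled |
|---|---|---|---|
| Any active vs none | 1/0.50 + 1/0.50 | 4 | 1 |
| One type vs none | 1/0.25 + 1/0.50 | 6 | 1.5 |
| Feedback vs suggestion | 1/0.25 + 1/0.25 | 8 | 2 |

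The missing contrasts are less precise than the primary one and more precise than the planned type contrast.

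**3. Illustrative standard errors.** Available points: 33 × 28 × 9 × 0.6 = 4,990, so about 2,495 with none and 1,248 (rounded) with each type. The standard error of a risk difference is sqrt[p(1-p)(1/n1 + 1/n2)]. The positive-sentiment rate p is not in the documents. I assume 40% and show 20% to 50%:

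| Contrast | p = 20% | p = 40% | p = 50% |
|---|---|---|---|
| Any active vs none | 1.1 points | 1.4 | 1.4 |
| One type vs none | 1.4 | 1.7 | 1.7 |
| Feedback vs suggestion | 1.6 | 2.0 | 2.0 |

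These ignore clustering within families and are on the risk-difference scale, whereas the SAP's coefficient is a log-odds ratio. Only their ordering should be relied on.

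**4. What pooling can hide.** Take illustrative positive rates of 0.40 (none), 0.50 (suggestion) and 0.35 (feedback).

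- Suggestion vs none: logit(0.50) - logit(0.40) = +0.405.
- Feedback vs none: logit(0.35) - logit(0.40) = -0.214.
- Pooled: the active rate is (0.50 + 0.35)/2 = 0.425, and logit(0.425) - logit(0.40) = 0.103.
- Feedback vs suggestion: logit(0.35) - logit(0.50) = -0.619.

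The pooled coefficient is mildly favourable although feedback does worse than none.

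**5. Can the type effects be recovered from the two planned contrasts?** With equal shares for the two types, each type's effect is about the pooled effect plus or minus half the type difference:

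- Suggestion: 0.103 + 0.619/2 = 0.413, against 0.405 directly.
- Feedback: 0.103 - 0.619/2 = -0.206, against -0.214 directly.

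The variance of this combination is 4 + 8/4 = 6 units, the same as for the direct contrast. So the point estimates can be rebuilt approximately, but the SAP does not plan this step.

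**6. Allocation.** At 9 decision points per day, 50% active gives 9 × 0.50 = 4.5 prompts. Item 5 of the Methods gives an average of 6, and 6/9 = 2/3 active. If that meant one third per condition, the pooled contrast would have 1/(1/3) + 1/(2/3) = 4.5 units and one type versus none 3 + 3 = 6, a ratio of 1.33. The centring and weights in the model depend on which allocation was used.

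**7. In families.** If the pooled contrast needs about 30 families, a type with the same effect against none needs about 44. Power at 33 families would be about 0.67 if the trial was sized at 80%, or 0.79 if at 90%. This uses the continuous-outcome formula and the assumptions of step 1, although the outcome is binary.

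**The case against.** The strongest reply is that nothing is lost. Each type is randomized against none, so both effects are estimable. The two planned contrasts nearly determine them (step 5), and means by condition give a direct descriptive comparison if the conditions are the three randomized ones, as item 5 of the Methods uses the word. The pooled contrast also answers a stated question: Objective and Analyses asks whether behavior differs according to whether a prompt was randomized or not, and the sample size rests on that comparison. Finally, this is a pilot that disclaims significance, so a rule that requires an interval to exclude zero would import the test that the SAP sets aside. At the power in step 7 (0.67 to 0.79), such a rule would also reject a useful type about 21% to 33% of the time.

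Most of this stands, and it rules out several stronger readings that a reader might infer:

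- *That the trial cannot answer its own question.* The data can answer it. What is missing is the specified analysis.
- *That a pooled result would lead to both types being kept or both dropped.* That follows only if the feedback-versus-suggestion result is ignored, and the SAP states no such rule. Effects of +8 and 0 points give pooled +4 and a difference of 8, which resolve back to +8 and 0. Effects of +5 and -5 give pooled 0 and a difference of 10, which resolve to +5 and -5.
- *That types will be judged by sign alone.* The SAP names means and user feedback beside direction.

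The reply does not supply the estimate that the decision needs. Combining the two contrasts is unplanned, approximate on the log-odds scale and dependent on equal shares for the two types, and its interval needs the covariance of the two coefficients. Means and standard deviations give no interval that respects clustering within 33 families. Pilot status is a reason to prefer intervals to tests, not a reason to omit the type-versus-none effects.

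**Conclusion.** The concern holds as a gap in the analysis plan, not as a flaw in the design. The two modelled contrasts do not directly estimate what Aim 2's inclusion decision needs, and no type-versus-none estimate with an interval is planned. The example in step 4 shows how far a pooled coefficient can depart from its parts: 0.103 against +0.405 and -0.214. Those rates are illustrative, not predictions.

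The price in precision is about 1.5 times the pooled variance under 50/25/25, or intervals about 1.22 times as wide (the square root of 1.5). This assumes similar outcome variance in each condition and effects that do not vary much between families. The documents do not support going further and treating the trial as uninformative about the separate types.

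**What to change.** 1. **Reconcile the allocation** between the SAP Overview (50/25/25, or 4.5 prompts per 9 points) and item 5 of the Methods (an average of 6), and state the probabilities that the software actually applied.
2. **Add suggestion versus none and feedback versus none** as causal excursion effects on the proximal outcome. Either enter two treatment indicators, each centred at its own randomization probability, or fit the existing model twice, each time dropping the other type's decision points and using the conditional probability. Under 50/25/25 that is 0.25/(0.25 + 0.50) = 1/3.
3. **Report each with a 95% cluster-robust interval**, and name these as the estimates that inform Aim 2 inclusion, alongside user feedback. Keep the pooled effect as the overall summary and feedback versus suggestion as the comparison between types.
4. **State in the SAP that the intervals describe precision** and are not significance tests, and that they will be wider than the pooled one. Complete the sentence on key outcomes in Primary Analysis so that the basis for inclusion is readable.
5. **If condition-level results have already been seen**, date the addition and label it as made afterwards.

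The cost is some SAP wording and two further model fits on data that the trial collects anyway. Families carry no added burden. The only drawback is the wider intervals.

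### The protocol promises a powered significance evaluation, the SAP disclaims it as too small a sample, and what the SAP uses instead gives the Aim 2 choice of micro-interventions no measure of uncertainty

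*Combined protocol and SAP*

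**What the plan says.** - **Purpose.** The protocol Overview says that the Aim 2 trial is to "determine which micro-interventions should be included in the refined intervention".
- **Objective and Analyses.** The trial will evaluate whether parent and child behaviour "is significantly different when the parent was randomized to receive the micro-intervention (prompt) or not". The hypothesis is that "the parent-child interaction will be more positive and less negative compared to when the parent was not provided feedback".
- **Justification for Number of Participants.** A formal power analysis assumes 28 days, a 50% randomization probability, 60% constant availability and "a decreasing linear trend of micro-intervention effects with a medium effect size". It arrives at 30 families, and "we aim to recruit $n = 33$ to ensure sufficient power". Significance level, target power and a numeric effect size are not stated.
- **SAP, Primary Comparison.** Either active type (suggestion or feedback, 25% each) is pooled and compared with no notification (50%). Feedback versus suggestion is examined second.
- **SAP, Primary Analysis.** The model accounts for clustering by participant. Then: "Analyses are not aimed at determining significance given the small sample size and the pilot nature of the research study". The next sentence reads "Direction of effects, means, and user feedback and key outcomes". It has no verb; I read it as saying that these are the key outcomes.

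The SAP mentions no confidence interval, threshold or rule for carrying a micro-intervention forward.

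**The concern.** The protocol and the SAP give opposite accounts of what the trial is for. One plans a powered evaluation of a difference. The other sets significance aside because the sample is small, although the planned 33 families exceed the 30 that the protocol calls sufficient. A reader of the results could not tell whether a reported p-value, or a missing one, follows the plan.

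The practical stake is the Aim 2 decision. A direction and a mean do not show how far chance alone could have produced them. The pooled primary contrast cannot separate the two types. The second contrast can rank them, but it does not show that either is better than no notification. As written, nothing limits the chance that an ineffective prompt type goes into the refined intervention.

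**Working it through.** **1. The plan's own figure (30 families).** This can be neither confirmed nor refuted, because significance level, power and numeric effect are missing. I used the standard micro-randomized-trial formula for a continuous outcome: noncentral F, linear effect falling to about zero, 28 days, randomization probability 0.5, availability 0.6, significance level 0.05 assumed.
- With 9 decision points a day, 30 families correspond to an average standardized effect of about 0.084 (80% power) or 0.096 (90% power).
- With 1 point a day, they correspond to about 0.25 (80%) or 0.29 (90%).
- If medium meant 0.5 to 0.55, about 6 to 14 families would be enough across 1 to 9 points a day.
- If 30 families give 80% power, 33 give about 84%.

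The SAP outcome is binary, so this is only an approximate check.

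**2. What a sign-only reading would do (illustration; the SAP states no such rule).**
- Pooled contrast, no true effect: P(favourable) = 0.50.
- Each type versus none, 50/25/25 allocation: variance is proportional to 1/0.25 + 1/0.5 = 6. The shared control gives covariance 1/0.5 = 2, so the correlation is 2/6 = 1/3.
- P(neither favourable) = 1/4 + asin(1/3)/(2π) = 0.250 + 0.054 = 0.304.
- P(at least one favourable) = 1 − 0.304 = 0.696, about 70%.
- If the effect is real, P(correct sign) = Φ(1.960 + z_power): 99.7% for an effect detectable with 80% power, 97.5% at 50% power, 87% at 20% power.

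Direction is therefore usually right when an effect of design size exists. It offers no protection when there is none.

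**3. Precision that intervals would show.** Ceiling on decision points: 33 × 28 × 9 × 0.6 = 4,990. This assumes that the 60% applies to 9 points a day and that every family records on all 28 days. The outcome rate p is assumed to be 0.3 to 0.5. Results are on the risk-difference scale.
- Pooled contrast: variance = p(1−p)/(0.25 × 4,990) = 0.000168 (p = 0.3) or 0.000200 (p = 0.5). Half-width = 1.96 × √variance = 2.5 to 2.8 points.
- Each type versus none: variance = 6p(1−p)/4,990. Half-width = 3.1 to 3.4 points.
- If the effect varies between families with SD s, add s²/33 and use t on 32 df (2.037).

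| Assumed SD of effect between families | Pooled half-width (points) | Each type vs none (points) |
|---|---|---|
| 0 (normal quantile) | 2.5 to 2.8 | 3.1 to 3.4 |
| 10 points | 4.4 to 4.6 | 4.8 to 5.0 |
| 20 points | 7.6 to 7.7 | 7.8 to 7.9 |

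- Lower yield: the SAP ties delivery to the first 30 minutes of a recording. If that left 4 points a day at 60% (assumed), 33 × 28 × 4 × 0.6 = 2,218 points. At p = 0.5 and no between-family variation, the pooled half-width would be about 4.2 points.

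**The case against.** A pilot may legitimately decline to test, and a sponsor who prefers estimation is not in error. That stands; it is a choice, and the fix allows it. Several stronger readings are tempting, and the documents do not support them.

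- **That the SAP selects by sign alone, so it cannot select or does so by coin toss.** No section states a sign-only rule. The SAP also names means and user feedback, and the protocol plans usability scales and an exit interview. The 50% and 70% figures describe a hypothetical rule with no true effect. They are not the plan's error rate.
- **That the plan throws away precision.** The planned model is clustered by participant and can supply standard errors and intervals. Nothing forbids reporting them. The gap is that the SAP does not commit to them or say how they will be used.
- **That calling the sample small is wrong because there are thousands of randomizations.** There are 33 clusters. With an assumed SD of 10 points and p = 0.5, the between-family part of the variance is 0.01/33 = 0.000303 against 0.000200 within families, about 60% of the total. Small is a fair description at family level, and 4,990 is a ceiling: the protocol says up to 9 opportunities a day, pays for two-thirds of the passive data, and drops invalid points.
- **That the sizing proves that a test would be well powered.** It cannot be reproduced from what is stated.

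It may also be said that Aim 3, a randomized comparison, limits the harm. In part it does. But as the Overview describes it, Aim 3 compares the programme with and without the micro-interventions as a set, so it would not isolate one ineffective type.

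**Conclusion.** The point holds in this form: the protocol's Objective and Analyses and its sample-size paragraph conflict with the SAP's Primary Analysis, and the outcomes that the SAP puts in place of a test carry no measure of uncertainty for the selection that Aim 2 has to make. The contradiction rests on the text alone. It does not touch the randomization or the data. It should be corrected because it leaves the plan incoherent and the selection unprotected against false inclusion.

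The interval widths rest on an assumed outcome rate, assumed between-family SDs and full recording, so they are planning values. They run from about 2.5 points to about 7.7 for the pooled contrast at the ceiling yield, and wider at lower yield. Whether to attach a p-value in a pilot is a trade-off and not part of this conclusion.

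**What to change.** 1. **Replace the SAP sentence that disclaims significance.** Suggested text: *The primary contrast (any micro-intervention versus none, positive sentiment), and feedback and suggestion each versus no notification, will be reported as estimates with two-sided 95% confidence intervals clustered by family, with a small-sample correction for about 33 clusters. The Aim 2 inclusion decision will be based on these intervals together with user feedback.*
2. **State in advance how the intervals will be read.** An interval without a reading rule does not by itself control false inclusion. For example, if a type had to have its lower limit above zero, the chance that at least one ineffective type passes would be at most 2 × 2.5% = 5% at nominal coverage. The price is that a type whose true effect equals the half-width would pass only about half the time. The sponsor should choose the rule with that in view.
3. **Reconcile the sections.** Either keep the powered test of the primary contrast in both protocol and SAP, and state its significance level, power and numeric effect; or declare estimation only, remove the significance wording ("is significantly different when the parent was randomized to receive the micro-intervention (prompt) or not") and the power claim ("we aim to recruit $n = 33$ to ensure sufficient power"), and give the expected interval width with its assumptions.

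**Cost.** Wording changes in the SAP and, on the estimation route, in two protocol sections. No new data and no new model are needed. A wide interval will have to be reported as inconclusive. The SAP refers to means provided in the registry and describes missingness as low, which suggests but does not prove that data were already in hand. If outcomes have been seen, the change must be labelled post hoc.
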